### **Sensitivity Analysis:**

#### ***Tipping point analysis:***

Tipping point analysis based on the same multiple imputation (MI) method as applied above will be performed to examine the robustness of the results from the primary analysis. A penalty  $\delta$  will be added to participants in efpeglenatide groups (4 or 6 mg) who have no HbA1c data at Week 56. The penalty will be gradually increased to evaluate at which level the conclusion of the analyses in terms of non-inferiority is changed for each efpeglenatide dose group. The tipping point is the penalty level at which the magnitude of efficacy reduction in participants without HbA1c data at Week 56 creates a shift in the treatment effect of efpeglenatide from the demonstration of non-inferiority to the failure of non-inferiority. The penalty  $\delta$  will start at 0 and increase by 0.1 (unit: %) at each imputation until UB of the 2-sided 95% CI for the adjusted mean difference is  $> 0.3\%$ . Least square mean difference between each efpeglenatide dose and dulaglutide and their associated 95% CI will be provided for each penalty level.

SAS pseudo-codes are provided in [Appendix A](#).

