# 1 OVERVIEW AND INVESTIGATIONAL PLAN

## 1.1 STUDY DESIGN AND RANDOMIZATION

This is a Phase 3, multicenter, 56-week, randomized, open-label for the drug (efpeglenatide and dulaglutide) and double-blind for the doses of efpeglenatide, active-controlled, 3-arm, parallel group study in participants with type 2 diabetes mellitus (T2DM) inadequately controlled with metformin.

After a Screening phase of up to 3 weeks, participants will be centrally randomized (using permuted block randomization schedule) via Interactive Response Technology (IRT) in a 1:1:1 ratio to 1 of the following 3 treatment groups:

- efpeglenatide 4 mg
- efpeglenatide 6 mg
- dulaglutide 1.5 mg

Randomization will be stratified by Screening hemoglobin A1c (HbA1c) ( $<8.0\%$ ,  $\geq 8.0\%$ ) and Visit 3 (Baseline, Day 1) body mass index (BMI) ( $<30 \text{ kg/m}^2$  and  $\geq 30 \text{ kg/m}^2$ ). Participants will receive open-label, active-controlled treatment for 56 weeks. Additional details on the study design and plan are provided in [Section 1.4](#).

Approximately 900 participants (300 participants per treatment group [details in [Section 1.3](#)] will be randomized.

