### 1.3 DETERMINATION OF SAMPLE SIZE

The sample size calculations are performed based on the primary endpoint, change in HbA1c (%) from Baseline to Week 56.

Assuming a common standard deviation of 1.1%, and the true difference between efpeglenatide and dulaglutide is zero, 300 participants per arm will ensure that the upper bound (UB) of the 2-sided 95% CI of the adjusted mean difference would not exceed 0.3% with 91% power.

Hence, there are 3 parallel dosing arms as follows:

- Efpeglenatide 4 mg, N=300
- Efpeglenatide 6 mg, N=300
- Dulaglutide 1.5 mg, N=300

[figure not shown]

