## **2.4.4 Analyses of efficacy endpoints**

Efficacy analyses will be performed on the ITT population using efficacy assessment collected during the study, including those obtained after IMP discontinuation and/or introduction of rescue therapy, unless otherwise specified (see [Section 2.5.4](#)).

Due to COVID-19 pandemic, participants may not be able to maintain their regular clinical visits according to the study protocol, with the closure of facilities, safety concern for the participants to go to the sites, unavailability of the investigators for treating participants, interruption of transportation or other COVID-19 related reasons. Data missingness due to these reasons is likely to be missing at random. For a continuous endpoint, all observed data of participants within the same treatment group can be used for imputation in an MAR approach. Sensitivity analyses will be performed to take into consideration of the impact of COVID-19 if the number of participants with missing endpoint data due to COVID-19 is above the threshold as specified in the following sections.

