#### **2.4.4.1 Analysis of primary efficacy endpoint**

##### **Hypothesis Testing of the Primary Endpoint:**

For the primary efficacy variable of change from Baseline to Week 56 in HbA1c, the following statistical null hypothesis and alternative will be tested as:

- H0: efpeglenatide - dulaglutide  $\geq$  0.3%
- H1: efpeglenatide - dulaglutide  $<$  0.3%

The null hypothesis will be tested at a 1-sided alpha level of 0.025 using a non-inferiority margin of 0.3%.

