##### **Primary Analysis:**

The statistical analysis for the primary endpoint is described below.

The Baseline value is defined in [Section 2.1.1](#).

Analysis of the primary efficacy endpoint (change from Baseline to Week 56 in HbA1c) will be performed using the ITT population, using HbA1c measurements obtained during the study, including those obtained after IMP discontinuation or introduction of rescue therapy.

The primary efficacy endpoint of change in HbA1c from Baseline to Week 56 will be analyzed with missing values imputed by BOCF-like MI method for both efpeglenatide and dulaglutide groups, under the MNAR framework:

- For participants with missing HbA1c values at Week 56, the missing values will be imputed using a random draw from a normal distribution with mean equal to their Baseline HbA1c and the standard deviation equal to the pooled standard deviation calculated from the square root of the mean square error estimated from a regression model with Baseline HbA1c as the dependent variable and randomization strata and treatment as the covariates.

In this analysis, missing endpoint values will be imputed 10 000 times to generate 10 000 data sets with complete data. Each of the complete datasets after the imputation will be analyzed by the ANCOVA model with the treatment groups (efpeglenatide 4 or 6 mg, dulaglutide 1.5 mg), randomization stratum of screening HbA1c ( $<8.0$ ,  $\geq 8.0\%$ ), Visit 3 (Day 1) BMI ( $<30$  and

$\geq 30 \text{ kg/m}^2$ ), and geographical region (North America, Eastern Europe (including Hungary and Poland)) as fixed effects, and baseline HbA1c value as a covariate.

In case a baseline value needed for multiple imputations is missing, it will be imputed by the population mean at Baseline.

SAS pseudo-codes are provided in [Appendix A](#).

Results from each complete dataset will be combined to provide the adjusted mean change in HbA1c from baseline to Week 56 (regardless of treatment discontinuation or initiation of rescue therapy) for each treatment group, as well as the between-group difference (comparing each efpeglenatide group versus dulaglutide group) and the 95% CI for the difference. This will be implemented using MIANALYZE procedure in SAS. If the UB of the 2-sided 95% CI for the adjusted mean difference (efpeglenatide versus dulaglutide) in HbA1c change from baseline to Week 56 is  $\leq 0.3\%$ , the noninferiority will be declared.

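### The tipping-point analysis shifts only missing efpeglenatide values, so it overstates robustness if dulaglutide has more missing Week 56 HbA1c

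*SAP*

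**What the plan says.** The primary analysis in SAP 2.4.4.1 has "missing values imputed by BOCF-like MI method for both efpeglenatide and dulaglutide groups, under the MNAR framework". Each missing Week 56 value is a "random draw from a normal distribution with mean equal to their Baseline HbA1c", so in every arm a missing participant is taken to have lost, on average, all benefit.

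The tipping-point analysis keeps that imputation and adds a penalty delta. The penalty "will be added to participants in efpeglenatide groups (4 or 6 mg) who have no HbA1c data at Week 56"; it starts at 0 and rises by 0.1 until the upper bound of the 95% CI passes 0.3%. Protocol 9.4.1, Table 5, has the same one-sided penalty. No step shifts missing dulaglutide values. The SAP reports the LS mean difference and CI at each penalty and sets no value above which the result counts as robust.

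Three other planned analyses do not tie dulaglutide to baseline:
- retrieved-dropout imputation with arm-specific models, with a back-up model if any arm has fewer than 5 retrieved dropouts;
- a completer analysis of observed values;
- if more than 10 endpoints are missing because of COVID-19, imputation of those values within arm under missing at random (SAP 2.4.4.1.1).

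**The concern.** In a noninferiority comparison, the assumption about missing data that helps the test drug is that missing comparator participants did badly. The sweep stresses the other side only: it makes missing efpeglenatide participants worse than baseline and leaves the comparator assumption alone. If missing dulaglutide participants in fact kept part of their HbA1c fall, the true difference would be closer to the margin than the primary analysis shows, and no step of the sweep would reveal by how much.

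The two axes also mean different things. A delta of 0.8 says that missing efpeglenatide participants end 0.8% above baseline. A gamma of 0.8 says that missing participants on an active drug kept a 0.8% fall. The second may be easier to believe, yet only the first is reported. Both efpeglenatide doses are compared with the same dulaglutide arm, so an error in this assumption moves both contrasts in the same direction.

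**Working it through.** All HbA1c figures are in percentage points.

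**Inputs from the documents.** Hypothesis: "The null hypothesis will be tested at a 1-sided alpha level of 0.025 using a non-inferiority margin of 0.3"%. Planning: "Assuming a common standard deviation of 1.1%, and the true difference between efpeglenatide and dulaglutide is zero". Allocation: "in a 1:1:1 ratio to 1 of the following 3 treatment groups", 300 per arm. **Not in the documents, hence assumed:** missing rates (5% to 30%), the dulaglutide change (−1.2 or −1.3), baseline SD (0.85) and imputation SD (about 0.6).

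**1. The plan's own figure.** SE = 1.1 × √(2/300) = 0.0898. Power = Φ(0.3/0.0898 − 1.96) = Φ(1.38) = 91.6%, which agrees with the SAP's statement that the upper bound "would not exceed 0.3% with 91% power". The CI half-width is 1.96 × 0.0898 = 0.176, so an estimated difference of 0 leaves headroom H = 0.3 − 0.176 = 0.124.

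**2. Distance to failure on each axis.** A penalty delta on efpeglenatide raises the difference by mE × delta. A retained fall gamma on dulaglutide raises it by mD × gamma. Holding the SE constant, delta* = H/mE and gamma* = H/mD, so delta*/gamma* = mD/mE.

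| H | mE / mD (assumed) | delta* | gamma* |
|---|---|---|---|
| 0.07 | 5% / 15% | 0.07/0.05 = 1.4 | 0.07/0.15 = 0.47 |
| 0.07 | 5% / 10% | 1.4 | 0.07/0.10 = 0.70 |
| 0.124 | 10% / 10% | 1.24 | 1.24 |
| 0.124 | 15% / 15% | 0.83 | 0.83 |
| 0.124 | 20% / 20% | 0.62 | 0.62 |
| 0.124 | 30% / 30% | 0.41 | 0.41 |

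H = 0.07 corresponds to an upper bound of 0.23.

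**3. Simulation of the planned imputation** (ANCOVA adjusted for baseline, Rubin pooling, 200 imputations, step 0.1, dulaglutide change −1.3):

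| mE / mD | Difference in observed values | Primary upper bound | delta* | gamma* |
|---|---|---|---|---|
| 10% / 10% | 0 | 0.169 | 1.2 | 1.4 |
| 15% / 15% | 0 | 0.175 | 0.8 | 0.9 |
| 10% / 20% | 0.2 | 0.223 | 0.8 | 0.5 |
| 10% / 20% | 0.1 | 0.134 | 1.5 | 0.9 |
| 5% / 15% | 0.1 | 0.135 | 2.9 | 1.2 |

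The ratios in the last three rows are 0.8/0.5 = 1.6, 1.5/0.9 = 1.7 and 2.9/1.2 = 2.4, against 2, 2 and 3 from the formula. The gap arises because a penalty widens the SE and a retained fall narrows it (at 15%/15%, 0.095 with delta 0.8 against 0.085 with gamma 0.8). So mD/mE is the right order but somewhat too large.

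**4. Joint shift.** At 15%/15% with an observed difference of 0, failure on the planned axis alone needs delta 0.8. Delta 0.4 together with gamma 0.4 already gives an upper bound of 0.296, and 0.65 with 0.65 gives 0.373.

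**5. How often it would matter.** Simulated trials with 300 per arm, SE 0.092, dulaglutide change −1.2 and 5%/15% missing. If missing dulaglutide participants keep −1.2, the difference rises by 0.15 × 1.2 = 0.18.
- True difference 0, the planning value: about 24% of trials that pass noninferiority are overturned.
- True difference 0.3, the margin itself: about 30% of trials pass. Of these, 44% to 48% (repeat runs) have a planned tipping point above +1.0, and 99% are overturned.

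**The case against.** **Unequal missingness is assumed, not predicted.** The drug is open-label, so differential dropout cannot be excluded, but nothing in the documents points to more of it on dulaglutide. With equal rates a small gamma* goes with an equally small delta*, and the planned sweep would already show a fragile result. This stands, and the point is conditional on it.

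**The 99% figure is a boundary case.** It takes the true difference to be the margin, where passing trials pass narrowly. The 24% at the planning value is the fairer figure. This also stands.

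**Other analyses would raise the alarm.** In the scenario on the margin, an estimate from observed data or from same-arm imputation fails noninferiority in about 92% of the trials that pass the primary analysis. That is a good part of the answer, with limits. Each such analysis gives one estimate, the completers are a selected group, and the COVID-19 analysis covers only COVID-19 cases. None gives a range for the comparator assumption.

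**Retention on dulaglutide alone is one-sided too.** True: with delta at 0 and gamma above 0, missing efpeglenatide participants keep nothing. That column is a stress test, not an expected case.

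A reader might go further and infer three things that the documents do not support:
- *That the plan will declare noninferiority robust when it is not.* The SAP sets no robustness threshold and prints the CI at every penalty.
- *That the SAP contradicts itself by stating* "Data missingness due to these reasons is likely to be missing at random". That sentence concerns COVID-19 reasons only, and SAP 2.4.4.1.1 acts on it in every arm.
- *That dulaglutide is held fixed at baseline.* Its missing values are random draws centred there, and efpeglenatide gets the same rule.

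**Conclusion.** The point holds as a conditional one. The planned sweep varies one arm's assumption, and the assumption it leaves alone is the one that can favour the test drug. If dulaglutide has more missing Week 56 values, the reported tipping point overstates robustness by about mD/mE: threefold by the formula at 5%/15%, and 2.4-fold in the simulated 5%/15% case. If the rates are similar, the two distances are nearly the same. What is then lost is the joint picture, and the chance to judge a retained effect on an active drug separately from a value worse than baseline.

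The sizes rest on assumed missing rates and an assumed dulaglutide change. The actual rates will also depend on the analysis set: SAP 2.3.1.2 moves efficacy to the mITT population after early termination, while 2.4.4.1 still names ITT. The primary test and its decision rule are not in question. This is a cheap improvement to a sensitivity analysis.

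**What to change.** Make the tipping point two-way in SAP 2.4.4.1:
- Cross the efpeglenatide penalty delta (0 upward in steps of 0.1) with a dulaglutide shift gamma. Let gamma run from 0 to the observed mean Week 56 change among dulaglutide participants with data, also in steps of 0.1.
- For each dose, report the upper bound of the 95% CI in every cell.
- State the gamma that overturns noninferiority at delta = 0, labelled as a stress test.
- Mark the cells in which missing participants in both arms retain an effect. With delta from 0 upward there are none, so add rows with delta below 0, down to the observed efpeglenatide change.
- Show the missing rate in each arm beside the grid, so that the reader can see whether the two axes should differ.

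The imputed data sets can be reused with shifts added, so no new data are needed. The cost is SAP wording, code and computing time. The downside is that the reported robustness may look less favourable than a single penalty would suggest.

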***Retrieved-dropout multiple imputation method:***

The retrieved-dropout multiple imputation sensitivity analysis will have 2 separate parts as follows:

1. Missing endpoint data in participants who prematurely discontinue the study treatment before the Week-56 visit will be imputed using a model built separately in each arm and estimated from participants in the same treatment arm who prematurely discontinue the study treatment before the Week-56 visit but have the measurement for the endpoint (retrieved dropouts). Considering that the number of participants in each treatment arm who discontinue the study treatment but have the measurement for the endpoint is expected to be small, a simple imputation model will be used, where only the Hb1Ac baseline measurements are included as the predictor. Each treatment group will have their own imputation model.
2. Missing endpoint data in all participants who stay on the study treatment until the Week-56 visit will be imputed using a model built separately in each arm and estimated from participants in the same treatment arm who stay on the study treatment until Week-56 visit and have the endpoint measurement, where randomization strata and Hb1Ac baseline measurements are included as the predictors.

In both parts, the missing data will be imputed using the regression method. After imputation, the completed data sets will be analyzed using an ANCOVA model similar to the primary analysis.

If there are no sufficient data to support the imputation approach in item 1 described above (less than 5 participants in any arms who prematurely discontinue the study treatment before the endpoint visit but have the measurement for the endpoint), a back-up method will be used. In particular, missing endpoint data in all participants, regardless of staying on the study treatment or not, will be imputed using a model built separately in each arm and estimated from participants in the same treatment arm with endpoint data, where randomization strata and corresponding baseline values are included as the predictors.

SAS pseudo-codes are provided in [Appendix A](#).

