#### **2.3.1.2 Modified Intent-to-treat population**

Due to the study terminated early by sponsor on September 9, 2020 (hereinafter referred to as “early termination”), the efficacy analyses will be performed in mITT population instead of ITT population originally planned. The mITT population is defined as,

- Participants who have completed the study treatment, or
- Participants who discontinued the study treatment AND completed/discontinued the study before the early termination, or
- Participants who discontinued treatment before early termination and discontinued the study due to early termination within 30 days of the target Week 56 visit (Day 392), or
- Participants who discontinued treatment due to early termination within 30 days of the target Week 56 visit (Day 392).

Participants will not be included in mITT if they discontinued study due to termination and discontinued study treatment (before or due to early termination) and had visits performed more than 30 days before the target Week 56 visit (Day 392).

By-visit summary will be provided for ITT population in addition for mITT population.

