### ***Efficacy data at Week 30 / Week 56***

The scheduled measurements at the endpoint visit (Week 30 or Week 56) as collected will be used in the efficacy analyses including those obtained after IMP discontinuation and/or introduction of rescue therapy. For participants whose efficacy measurement is not available at the endpoint visit, the measurement at unscheduled visit (including the end of treatment and/or study visit for those prematurely discontinued) will be used if the unscheduled measurement is within +/-30 days (7 days for FPG and SMPG) of the date of the end point visit [targeted study Day 210 for Week 30 (or Day 392 for Week 56)]. If multiple measurements are associated to the same targeted date, the closest to the targeted study day will be used. In case of equality, the last measurement will be used. If there are still no measurements for a given parameter at an endpoint visit, the data is considered missing for efficacy analyses, where multiple imputation would be applied as appropriately as described in [Section 2.4.4.1](#).

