**Sensitivity analysis using retrieved-dropout multiple imputation method:**

1. Multiple imputations in participants who prematurely discontinued the study treatment before the Week-56 visit:

```
proc mi data=data_IN out=data_OUT_DISC nimpute=10000 seed=14829;  
  where PEOT56FL = "Y";  
  by ARM;  
  var BASE AVAL_W56;  
  monotone regression (AVAL_W56= BASE );  
run;
```

2. Multiple imputations in participants who stay on the study treatment until the Week-56 visit:

```
proc mi data=data_IN out=data_OUT_COMPL_MI nimpute=10000 seed=14829;  
  where PEOT56FL='N';  
  by ARM;  
  class HbA1c_strata BMI_strata;  
  var HbA1c_strata BMI_strata base AVAL_W56;  
  monotone regression (AVAL_W56 = HbA1c_strata BMI_strata BASE );  
run;
```

3. Combine multiple imputations from the step 1 and step 2 above

```
Data dataMI;  
set data_OUT_DISC  
    data_OUT_COMPL_MI  
run;
```

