**Back-up plan:**

```
proc mi data =data_IN out=data_OUT_MI nimpute=10000 seed=14829;  
  by ARM;  
  class HbA1c_strata BMI_strata;  
  var HbA1c_strata BMI_strata base AVAL_W56;  
  monotone regression (AVAL_W56 = HbA1c_strata BMI_strata BASE );  
run;
```

In this sample SAS® (version 9.4) code:

- DATA\_IN is the input dataset including one observation per participant in the ITT population with Baseline HbA1c value and change from baseline at Week 56.
- data\_OUT\_DISC is the output dataset including observed and imputed data for participants who have prematurely discontinued the treatment.
- data\_OUT\_COMPL\_MI is the output dataset including observed and imputed data for all participants who have completed the 56-week study treatment period.
- Data\_OUT\_MI is the output dataset including observed and imputed data for all participants using backup plan.
- PEOT56FL is the variable indicating whether the participant prematurely discontinued the study treatment (PEOT56FL="Y" if the participants prematurely discontinued the study treatment before Week 56 visit and PEOT56FL="N" if the participant stay on the study treatment until Week 56 visit).
- ARM is the randomized treatment group (Dulaglutide 1.5 mg, Efpeglenatide 4mg, Efpeglenatide 6mg).
- HbA1c\_strata is the randomization stratum of screening Hb1Ac (<8%, ≥8%)
- BMI\_strata is the randomization stratum of BMI at Visit 3(<30, ≥30)
- BASE is the baseline HbA1c.
- AVAL\_W56 is the HbA1c at Week 56.
- The seed (14829) has been chosen arbitrarily and is based on the study code (EFC14829).

**Sensitivity analysis** (*If more than 10 missing endpoint data impacted by COVID-19*):

**Step 1:** Perform regression to estimate pooled mean and standard deviation of non-missing baseline HbA1c measures

```
proc glm data=BaseHbA1c;
    class ARM HbA1c_strata BMI_strata;
    model base = ARM HbA1c_strata BMI_strata;
    ods output FitStatistics=basefit;
run;

proc sql noprint;
    select RootMSE, depmean
    into :std, mean
    from basefit;
quit;

data base_imputed;
    set InputData;
    if base = . then newbase = &mean; /* in case of missing baseline HbA1c measure, pooled mean is used as the
baseline HbA1c*/
    else newbase = base ;
run;
```

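### The retrieved-dropout flag ignores why treatment stopped, so participants stopped by the sponsor's termination near Week 56 are classed as retrieved dropouts although their HbA1c is largely on-treatment

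*SAP*

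**What the plan says.** SAP 2.4.4.1 splits the imputation in two. Part 1 handles participants who stopped treatment early. It is fitted separately in each arm, with baseline HbA1c as the only predictor, on donors "who prematurely discontinue the study treatment before the Week-56 visit but have the measurement for the endpoint (retrieved dropouts"). Part 2 handles participants who stayed on treatment and is fitted on others who did so.

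Appendix A implements the split with PEOT56FL. Step 1 is headed "Multiple imputations in participants who prematurely discontinued the study treatment before the Week-56 visit" and selects PEOT56FL = Y. The flag is Y "if the participants prematurely discontinued the study treatment before Week 56 visit". The note on the part 2 output dataset describes it as "all participants who have completed the 56-week study treatment period".

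A back-up replaces part 1 if there are "less than 5 participants in any arms who prematurely discontinue the study treatment before the endpoint visit" with an endpoint value. It imputes every missing value from a model "estimated from participants in the same treatment arm with endpoint data", whatever the treatment status.

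Two other rules bear on this. SAP 2.3.1.2 moves the efficacy analyses to a modified ITT (mITT) population. Separately from treatment completers, it lists "Participants who discontinued treatment due to early termination within 30 days of the target Week 56 visit (Day 392"). SAP 2.5.4 says that, when no scheduled Week 56 value exists, "the measurement at unscheduled visit (including the end of treatment and/or study visit for those prematurely discontinued) will be used" if it lies within 30 days either side of Day 392.

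**The concern.** A retrieved-dropout analysis is useful because its donors were off treatment when measured: their values stand in for those of participants who stopped and were not measured. A participant whom the sponsor stopped in the last weeks, and who was sampled soon afterwards, is a different case. That HbA1c mainly reflects treatment. If such people are donors, values imputed for true dropouts are pulled toward the on-treatment level, and the check looks more like an off-treatment analysis than it is.

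The fewer-than-5 rule uses the same undivided count. An arm with 4 true retrieved dropouts and 1 termination stop reaches 5, so the back-up is not used. The flag also misdirects the other way: a termination stop with no windowed HbA1c would be imputed from true dropouts.

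This is not text left over from before the termination. The SAP change table (1.6) shows that version 2 added the mITT and the retrieved-dropout method together, giving the early termination as the reason.

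**Working it through.** **Planning figure.** SAP 1.3 gives SD 1.1, 300 per arm, true difference 0 and margin 0.3. SE = 1.1 × √(2/300) = 0.090. Power = Φ(0.3/0.090 − 1.96) = 91.6%, against the stated 91%. The figure reproduces and is not in dispute. It gives the scale: margin 0.3, planned SE 0.09.

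**Tracing one participant.** The sponsor's termination stops treatment on Day 370, and HbA1c is taken at the end-of-treatment visit.
1. mITT (2.3.1.2): included, under the termination category and not as a completer.
2. Week 56 value (2.5.4): the window is 392 ± 30, Day 362 to 422, so the sample counts.
3. Flag (Appendix A): treatment stopped before the Week 56 visit, so PEOT56FL = Y. Neither 2.4.4.1 nor the code refers to the reason.
4. Result: Y with an observed endpoint, hence a part 1 donor and one of the 5.

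**How on-treatment is the value?** Protocol 1.3, footnote a, asks for the visit as soon as possible after the last dose, and Protocol 3.1 gives HbA1c a memory of 120 days. Weighting days equally (a simplification), a sample 7 days after the last dose is 113/120 = 94% on-treatment; at 30 days it is 90/120 = 75%.

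**Size.** The documents give no count of termination stops or retrieved dropouts, no on/off-treatment gap and no missingness by arm. All inputs below are assumed.
- Pull on imputed values, toward lower HbA1c = w × g, where w is the termination share of donors and g the gap (0.5 to 1.1 points).
- Between-arm shift = (mE − mD) × w × g, where mE and mD are the shares imputed by part 1 in the efpeglenatide and dulaglutide arms, with w equal in both.

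*(a) Every arm has at least 5 true retrieved dropouts*

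| True + termination donors | w | Pull | Shift, 10%/10% imputed | Shift, 15%/5% | Shift, 10%/7% |
|---|---|---|---|---|---|
| 8 + 3 | 3/11 = 0.273 | 0.14–0.30 | 0 | 0.014–0.030 | 0.004–0.009 |
| 8 + 8 | 8/16 = 0.50 | 0.25–0.55 | 0 | 0.025–0.055 | 0.008–0.017 |

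A simulation (300 per arm, regression on baseline, then ANCOVA, 2000 runs) agrees. For 8 + 8 at 15%/5% the shift is −0.024 (g = 0.5) and −0.056 (g = 1.1). The sign favours efpeglenatide when efpeglenatide has more missing data.

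If the donor mix differs by arm, the shift is m × (wE − wD) × g. With 50% v 20% and 5% to 10% imputed, it is 0.05 × 0.3 × 0.5 = 0.008 to 0.10 × 0.3 × 1.1 = 0.033. At 70% v 0% with 10% imputed it is 0.035 to 0.077, so 0.06 is not a ceiling.

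*(b) An arm has fewer than 5 true retrieved dropouts*
- As written, 3 + 2 (w = 0.40) pulls by 0.20–0.44, and 1 + 4 (w = 0.80) by 0.40–0.88.
- With termination stops removed, the back-up applies in every arm. Assuming 150 to 250 on-treatment completers per arm, the on-treatment donor share is 152/155 = 98.1% to 254/255 = 99.6%. The pull is 0.49–1.10, larger than before. At 15%/5% the between-arm shift is 0.049–0.110.

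**The case against.** **The remedy does not match the mechanism.** What makes a value near on-treatment is days since last dose, not the reason for stopping. This stands in part. A reader might infer that re-flagging removes the contamination. That would hold only if nobody stopped for another reason close to Day 392, and the documents do not say so. Re-flagging removes the termination source only.

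**The remedy may make the check less informative.** The SAP itself expects few retrieved dropouts, and one arm below 5 switches all arms to the back-up. This stands, as case (b) shows.

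**The group may be small or empty.** If last doses fell on 9 September 2020 (an assumption, because the SAP dates the termination and not each last dose), a last dose on Day 362 to 386 means a first dose between 21 August and 14 September 2019, about 25 days of enrolment. This is fair, and it is why the point is worded as what the rules allow.

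**SAP 2.5.4 may already cover it.** The early-discontinuation rule maps the visit of someone who stops at or just before a scheduled visit to that visit, so a programmer might set such people to N. But the rule maps values and leaves the flag alone. The Week 56 visit window is only ±5 days, and the Appendix A note describes part 2 as treatment completers. Two programmers could reasonably differ.

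**Reasons are listed anyway.** SAP 2.2 tabulates reasons for discontinuation. The planned missing-data assessment reports Week 56 availability by treatment status only, so donors by reason would have to be reconstructed.

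**Conclusion.** The point holds as a misclassification in the stated rules. Participants whom the sponsor stopped within 30 days of Day 392 are classed as retrieved dropouts; they can enter the part 1 donor model and count toward the minimum of 5, although their HbA1c is largely on-treatment.

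The size cannot be determined from the documents. With equal donor shares across arms and the assumed gaps and missingness above, the between-arm shift is about 0 to 0.06 points against the 0.3 margin. It is zero when missingness is also balanced.

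A reader might infer that the non-inferiority conclusion is at risk. The documents do not support that: the primary BOCF-like imputation and the tipping-point analysis use neither PEOT56FL nor these donors. Nor do the documents show that any such participant exists. Severity is minor.

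A related gap remains in the input data. Appendix A describes the input to this analysis as the ITT population, while 2.3.1.2 moves efficacy to the mITT. Run on the ITT, participants whom the termination stopped more than 30 days before Day 392 would also be flagged Y and, lacking a windowed value, imputed from part 1.

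**What to change.** - State that this sensitivity analysis is run on the mITT, and align the Appendix A input description.
- Set PEOT56FL = N (part 2) when the recorded reason for stopping is the sponsor's termination within the 30-day window. Correct the note that describes part 2 as completers only.
- Apply the fewer-than-5 rule to the retrieved dropouts that remain.
- Report donor counts per arm by reason for stopping and by days from last dose to the HbA1c sample. The second split shows the late stops for other reasons that stay in the donor set.
- If the back-up is triggered, label it a missing-at-random analysis, state that no retrieved-dropout check was feasible, and rely on the tipping-point analysis for robustness.

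The cost is SAP wording, one flag derived from discontinuation reasons already collected, and one small table. The downside is a greater chance of triggering the back-up. In that case the change corrects the label but does not reduce the pull toward on-treatment values.
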